Engaging Medically Complex Veterans in Tele-Rehabilitation Using a Biobehavioral Approach: A Pilot Study of Feasibility and Acceptability

NCT04942613

July 14, 2022

COMIRB Protocol

COLORADO MULTIPLE INSTITUTIONAL REVIEW BOARD
[name] [contact] [contact]

Protocol #: 21-2773

Project Title: Engaging Medically Complex Veterans in Tele-Rehabilitation Using a Biobehavioral Approach: A Pilot Study of Feasibility and Acceptability

Principal Investigator: [name] [name]

Version Date: 07.14.2022

I. Hypotheses and Specific Aims:

This is a single-site, randomized pilot study using a two-group (GROUP1 and GROUP2) crossover design. Fifty Veterans with medical complexity and deficits in physical function will participate. Outcomes will be assessed at baseline (pre-intervention), 6 weeks (intervention mid-point), 12 weeks (end of intervention), and 24 weeks.

AIM 1: To determine the feasibility and acceptability of a multicomponent telerehabilitation program.

Hypothesis 1a: 75% of Veterans will achieve $\geq 80\%$ adherence as measured by attendance.

Hypothesis 1b: At least 75% of Veterans will perceive the program as acceptable ($\geq 4/5$ on Acceptability of Intervention Measure¹³) and feasible ($\geq 4/5$ on Feasibility of Intervention Measure). In addition, we will monitor adverse events and categorize severity (mild, moderate, severe) and relatedness (definitely, probably, possibly).

AIM 2: To assess the preliminary response of a multicomponent telerehabilitation using a two-group randomized crossover design and determine variability estimates. Outcomes for this aim are accelerometer-based physical activity, physical function, quality of life, and loneliness.

Hypothesis 2: At program end (GROUP1 12 weeks, GROUP2 24 weeks), participants will have a trend of improved outcomes (accelerometer 7-day average step count with ActiGraph physical activity monitors (ActiGraph Inc. Pensacola FL, primary) compared to program start (GROUP1 baseline, GROUP2 12 weeks). In addition, using the pooled intervention sample, variability estimates (standard deviation), will be determined for change in physical activity, physical function (,30 second sit to stand¹⁴) and self-report measures of physical function (Activity Measure for Post-Acute Care¹⁵), quality of life (PROMIS 29 Profile v2.0¹⁶), and loneliness (3-item loneliness scale¹⁷ Berkman Social Disengagement Scale¹). This will allow for sample size estimates for the subsequent larger effectiveness trial.

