This new line of research builds on the collective experience of the investigative team. The PI and Co- Investigators have worked together over the past 7 years to 1) develop progressive rehabilitation strategies for medically complex patients (VA RR&D I21 RX002054, VA RR&D I01 RX001978), 2) develop and test biobehavioral strategies to improve physical activity for patients following dysvascular lower limb amputation⁸ and total knee arthroplasty,⁹ and 3) test and refine telerehabilitation delivery for patients following total knee arthroplasty (NIA R44 AG055341). This study will be the first to combine these lines of research into a coherent multicomponent program. Further, this is the first study to determine the safety and feasibility of telerehabilitation approaches for a high-risk, medically complex population. The investigative team's collective experience and ongoing work in these areas positions them uniquely to lead the proposed investigation.

IV. Research Methods

C.1 Outcome Measures:

Aim 1: Feasibility outcomes provide information to help determine if a larger study should be performed. Feasibility includes adherence, acceptability, and safety, and satisfaction. Additional factors may influence feasibility, and the following surveys for will be assessed

at program end for Veterans and therapists: Feasibility of Intervention Measure,¹³ Acceptability of Intervention Measure,¹³ Intervention Appropriateness Measure.¹³ Satisfaction is measured by V-signals which is a survey specific to the VA; it measures satisfaction associated with telerehabilitation services. Additionally, we will monitor recruitment rate (proportion of Veterans enrolled out of those screened) and retention (proportion of Veterans who complete program out of all enrolled) to inform feasibility of a larger randomized controlled trial for effectiveness.

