Based Primary Care, and inpatient and outpatient rehabilitation settings. Potential Veterans with whom we have a treatment relationship will be pre-screened through standardized chart review followed by standardized phone screen. If eligible and interested in participating, Veterans will provide informed consent and be enrolled in the study; once enrolled, they will be randomized to either a waitlist control (GROUP2) or experimental (GROUP1) group. Participants will complete surveys and direct observation (Aims 1 & 2). Veterans will also undergo performance-based assessments of physical activity and physical function and complete self-reported measures for physical function, quality of life, loneliness, social support, and mental health.

Formal Inclusion/Exclusion Criteria

Inclusion

- ≥ 60 years of age
- Multiple chronic conditions (Functional Comorbidity Index⁶⁸ ≥ 3)
- Impaired physical function (≤ 10 on 30 second sit to stand)

Exclusion

- Life expectancy < 12 months
- Acute or progressive neurological disorder (e.g., Amyotrophic Lateral Sclerosis, recent stroke)
- Moderate to severe dementia without caregiver assistance (< 18 on telephone Montreal Cognitive Assessment (T-MoCA)⁶⁹)
- Unstable medical condition precluding safe participation in progressive rehabilitation (e.g., unstable angina) as defined by ACSM guidelines

We plan to randomize 50 Veterans (25 randomized to each group), with the goal of having 40 Veterans complete the study (20% attrition rate). Due to our enrollment process, we plan to have 70 Veterans sign the informed consent; this will allow for up to 20 Veterans to complete evaluation but be found ineligible based on identified exclusion criteria. The goal of the study is to obtain a representative sample of older Veterans at risk for, or presenting with, impaired physical function contributing to fall risk, physical dependence, and risk for hospitalization. Both sexes and all races are included in the study, however the Veteran population is predominantly male and Caucasian, which will be reflected in the enrollment.

D. Study Design and Research Methods

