Social Support: Social support is a key component of our program to address social isolation and perceptions of loneliness. We will foster a sense of community and family among Veterans enrolled in the program through virtual group telerehabilitation sessions and group discussions. During group telerehabilitation, therapists will purposefully engage Veterans, providing encouragement on performance while also facilitating peer support and encouragement. The group discussions, which occur at the end of group telerehabilitation sessions, will have core components to reinforce biobehavioral strategies and allow Veterans to share their experiences, successes, and struggles implementing our program. Group discussions will be iterative by encouraging Veterans to suggest topics for discussion and ideas for improvement.

Outcomes: All outcomes will be evaluated by a blinded assessor. **Aim 1:** Feasibility outcomes provide information to help determine if a larger study should be performed. Feasibility includes adherence, acceptability, and safety, and satisfaction. Additional factors may influence feasibility, and the following surveys will be assessed at program end: Feasibility of Intervention Measure,¹³ Acceptability of Intervention Measure,¹³ Intervention Appropriateness Measure.¹³ Satisfaction is measured by V-signals which is a survey specific to the VA; it measures satisfaction associated with telerehabilitation services. Additionally, we will monitor recruitment rate (proportion of Veterans enrolled out of those screened) and retention (proportion of Veterans who complete program out of all enrolled) to inform feasibility of a larger randomized controlled trial for effectiveness.

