Heterogeneity of medically complex older adults: Medically complex older adults are heterogeneous in age, cognitive status, medical status, psychological comorbidity, living environment, and social support.²² Additionally, they experience acute exacerbations of chronic conditions impacting their response to treatment and contributing to high drop-out rates among this population. To accommodate for this from our experiences, we anticipated a higher attrition rate (20%) and adjusted enrollment accordingly.

G. Data Analysis Plan:

Analysis Plan. Analyses will be performed in SAS v 9.4 or above and hypothesis tests will be two-sided, assuming an alpha level of 0.05. Participant characteristics and outcome variables will be summarized using means, standard deviations (SD), medians, ranges, N and percent, as appropriate.

Aim 1. The percent of Veterans (1) achieving $\geq 80\%$ adherence and (2) scoring $\geq 4/5$ on the Acceptability of Intervention Measure will be calculated with associated 95% exact binomial confidence intervals. We will additionally calculate the proportion of adverse events that are found to be possibly, probably, or definitely related to the intervention.

Aim 2. Given the small samples, the median change from baseline to 12 weeks for those randomized to the intervention will be compared between the groups using a Wilcoxon rank-sum test for each outcome of interest (7-day average step count as primary). Estimates of variability (SD) in the change from pre to post-intervention for the pooled sample completing the intervention (N=40) will be calculated for each outcome and reported with 95% CIs. These estimates and the CIs will inform sample size calculations for a future effectiveness trial.

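### Does leaving the Feasibility measure out of the Aim 1 threshold sentence stop the plan from settling Hypothesis 1b?

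*Combined protocol and SAP*

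**What the plan says.** In Section I, Hypothesis 1b states "At least 75% of Veterans will perceive the program as acceptable", defined as at least 4/5 on the Acceptability of Intervention Measure. The same sentence joins to this, with 'and', a perception of the program as feasible, defined as at least 4/5 "on Feasibility of Intervention Measure). In addition, we will monitor adverse events".

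The Feasibility measure is collected. Section C.1 lists it among the surveys given "at program end for Veterans and therapists: Feasibility of Intervention Measure", and the Outcomes paragraph of Section D repeats that "the following surveys will be assessed at program end: Feasibility of Intervention Measure". Both sections explain the purpose: "Feasibility outcomes provide information to help determine if a larger study should be performed".

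In Section G, the Aim 1 paragraph gives two threshold percents with exact intervals: adherence of at least 80%, which serves Hypothesis 1a, and at least 4/5 "on the Acceptability of Intervention Measure will be calculated with associated 95% exact binomial confidence intervals". It then adds the proportion of adverse events related to the intervention. The opening paragraph of Section G applies to all outcomes: "outcome variables will be summarized using means, standard deviations (SD), medians, ranges, N and percent, as appropriate".

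**The concern.** Hypothesis 1b has two halves, and the sentence written to analyse it names one. If Acceptability falls below 75%, 1b is missed on the point estimate whatever Feasibility shows. If Acceptability reaches 75%, the Aim 1 paragraph taken alone cannot say whether 1b is met. A favourable Acceptability figure with its interval might then be taken for the whole of 1b, while Feasibility falls short or appears without its uncertainty.

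There is a second ambiguity. If 1b requires the same Veteran to pass both scales, two separate percents need not determine the percent passing both, and the choice between a joint and a per-scale reading could be made after the data are seen. Aim 1 is the first aim of this pilot and informs the decision on a larger study, so the point deserved a check.

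**Working it through.** **Inputs.** The 75% target and the 4/5 cut-offs come from Hypothesis 1b. The Formal Inclusion/Exclusion Criteria section plans 50 randomized "with the goal of having 40 Veterans complete the study (20% attrition rate"). The stated size reproduces: 40 / (1 − 0.20) = 50. No power or precision figure is given for Aim 1. The pass counts below are assumed. So is n = 40 as the Aim 1 denominator; n = 50 is shown as the alternative.

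**Step 1: what the plan yields for Feasibility.** The survey is collected (C.1 and D), the cut-off and target are fixed (Hypothesis 1b), and outcome variables are summarized by N and percent (Section G, opening paragraph). Together these give the count and percent of Veterans at or above 4/5 on Feasibility. Not written down are an interval for that percent and a percent passing both scales.

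**Step 2: per-scale reading, judged on the point estimate.** The target is 0.75 × 40 = 30 Veterans on each scale. Take Acceptability 34/40 = 85.0% and Feasibility 28/40 = 70.0%. Feasibility is below 30, so 1b is not met, and the general summary alone shows it.

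The exact (Clopper-Pearson) interval for x of n has as limits the 2.5% quantile of Beta(x, n − x + 1) and the 97.5% quantile of Beta(x + 1, n − x). It depends only on x and n, so any reader can obtain it from the reported count:

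| Passes | Percent | Exact 95% CI |
|---|---|---|
| 28/40 | 70.0 | 53.5 to 83.4 |
| 34/40 | 85.0 | 70.2 to 94.3 |

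**Step 3: joint reading.** With *a* passes on Acceptability and *f* on Feasibility, the number passing both lies between max(0, *a* + *f* − 40) and min(*a*, *f*).

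| *a*, *f* | Joint count | Joint percent | Joint target of 30/40 |
|---|---|---|---|
| 34, 28 | 22 to 28 | 55 to 70 | missed |
| 30, 30 | 20 to 30 | 50 to 75 | open |
| 34, 34 | 28 to 34 | 70 to 85 | open |
| 35, 35 | 30 to 35 | 75 to 87.5 | met |

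With equal counts, the two percents leave the joint reading open from 30/40 through 34/40. The lower limits are worst cases in which no Veteran fails both scales. At 34/40 on each, six Veterans fail each scale and the joint count is 28 plus the number failing both. It falls below 30 only if at most one Veteran fails both.

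**Step 4: would an interval decide 1b?** No passage says that 75% is judged by a confidence limit. At 29/40 (72.5%) the exact interval is 56.1% to 85.4%; at 35/40 (87.5%) it is 73.2% to 95.8%. Both contain 75%. The intervals describe precision and do not decide the hypothesis.

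**Step 5: other denominator.** With n = 50, the first count at or above 75% is 38/50 = 76.0% (61.8% to 86.9%). The equal count that guarantees the joint target solves 2*a* − 50 ≥ 38, so *a* = 44, or 88%. The picture is the same.

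**The case for a change.** The strongest case for a change is that the authors did not rely on the general summary sentence for adherence or Acceptability. They listed those separately with exact intervals, so half of one hypothesis is handled less fully than the other half. The repair would cost two or three sentences and two table rows, with no new data. It would also fix the joint or per-scale choice before results are known.

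Much of this stands as description. The interval for Feasibility is unwritten, and the joint percent cannot be recovered from the two separate percents. The worst-case label does not remove the second point. At 34/40 on each scale, independent failures would give an expected overlap of 6 × 6 / 40 = 0.9 Veterans, short of the two needed, so the joint result would be in real doubt unless failures on the two scales tend to go together.

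It does not stand as a reason to amend. The open zone exists only if 1b is joint, and the documents do not say that it is. No passage lets Acceptability stand in for the whole of 1b. Because Hypothesis 1b names both scales, a report that left one out would be visibly incomplete. No formal go/no-go rule is attached to the result.

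**Conclusion.** This is a gap in detail that analysts can be expected to fill sensibly. The plan collects the Feasibility measure, fixes its cut-off and target, and summarizes it by count and percent. That is enough to settle 1b per scale on the point estimate, and the missing interval follows from the count. The remaining ambiguity is confined to a joint reading: with 40 respondents and equal counts, 30 to 34 passes on each scale.

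The conclusion rests on three assumptions: the general summary sentence covers the Aim 1 surveys, 75% is judged on the point estimate, and 1b is read scale by scale. The documents are compatible with all three but state none outright. For a descriptive pilot outcome with no decision rule attached, no change to the plan follows.

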We propose a pilot, two-arm randomized trial using a waitlist control to determine the feasibility, acceptability, and safety (AIM 1) of a 12-week multicomponent telerehabilitation program. We will also assess the preliminary response (AIM 2) to this 12-week intervention. Participants (n=50) will be randomized to GROUP1 or GROUP2 using computer-generated random blocks of 2 and 4, stratified by sex. A waitlist control (GROUP2) will be used to simultaneously achieve the aims and ensure that all participants receive the intervention. Data will be collected at baseline (pre-intervention),

6-weeks (intervention midpoint for GROUP1), 12 weeks (intervention end for GROUP1, primary endpoint), and 24 weeks.

Setting & Recruitment:

Following consent and prior to baseline assessment and randomization, each participant will complete a physical therapy evaluation performed by a licensed physical therapist. The purpose of this evaluation is to ensure the Veteran is appropriate for the planned intervention and is eligible for the study. The evaluation may include standard evaluation tasks including but not limited to chart review, subjective history, and functional assessment.

Initial evaluation, intervention, and testing will occur through telehealth via VA Video Connect using a site-to-home format. Dedicated telehealth rooms are available for the study team in the ECHCS GRECC. Veterans will have the option of using their personal device (e.g., tablet, computer) or a VHA-issued tablet.

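### The one adverse-event statistic named in Section G counts events, so it shows neither how many Veterans had a related event nor an upper limit on risk per Veteran

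*Combined protocol and SAP*

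**What the plan says.** Section D (Study Design and Research Methods) makes safety part of the first aim: the trial is to "determine the feasibility, acceptability, and safety (AIM 1) of a 12-week multicomponent telerehabilitation program". The Aim 1 outcome text repeats this: "Feasibility includes adherence, acceptability, and safety, and satisfaction". That text also says the feasibility outcomes help decide whether a larger study should follow.

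Under Hypothesis 1b in Section I, the investigators state that "we will monitor adverse events and categorize severity (mild, moderate, severe) and relatedness (definitely, probably, possibly"). Section E says that all adverse events are recorded, both during study activities and between them.

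In Section G, under Aim 1, adherence and acceptability are each a percent of Veterans that "will be calculated with associated 95% exact binomial confidence intervals". The safety sentence follows: "We will additionally calculate the proportion of adverse events that are found to be possibly, probably, or definitely related to the intervention". No interval is attached to it. A general sentence at the start of Section G allows outcome variables to be summarized by counts and percents where appropriate. It does not mention adverse events.

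**The concern.** A share of events answers the question: of the events recorded, what fraction was attributed to the program? Someone deciding on a larger trial also needs to know what fraction of Veterans had a program-related event, and how high that fraction could plausibly be. The planned figure answers neither part.

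It also varies with something other than program harm. Because all events are recorded, unrelated illness enters the denominator, and more unrelated illness lowers the figure while related harm stays the same. Section F says of this population that "they experience acute exacerbations of chronic conditions impacting their response to treatment", so unrelated events are plausible.

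If no event is attributed to the program, the planned figure is 0%, or undefined if no events occur at all. Section E expects exercise side-effects to be very infrequent, so few or no related events is a realistic outcome. That is when an upper limit is most useful.

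**Working it through.** **Inputs from the documents**
- Planned statistic: related events divided by all events (Section G, Aim 1).
- Interval method already chosen for Aim 1: exact binomial, 95% (Section G).
- 50 Veterans randomized, 25 per group, "with the goal of having 40 Veterans complete the study (20% attrition rate") (Formal Inclusion/Exclusion Criteria).
- Program end, from Hypothesis 2: "At program end (GROUP1 12 weeks, GROUP2 24 weeks"). Each Veteran's program period is therefore weeks 0-12 in GROUP1 and weeks 12-24 in GROUP2.

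The documents give no adverse-event counts, so all counts below are assumptions.

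**Step 1. Reproduce the plan's number.** 40 / (1 − 0.20) = 50. This agrees with the plan and gives the range of possible denominators, 40 to 50.

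**Step 2. Behaviour of the planned share.** With R related and U unrelated events, share = R / (R + U).

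| R | U | Share |
|---|---|---|
| 10 | 10 | 10/20 = 50% |
| 10 | 30 | 10/40 = 25% |
| 10 | 90 | 10/100 = 10% |
| 2 | 2 | 2/4 = 50% |
| 2 | 10 | 2/12 = 16.7% |
| 2 | 30 | 2/32 = 6.3% |

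Within each block related harm is constant. In the first block the share falls fivefold.

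**Step 3. Same events, different numbers of Veterans.** The exact 95% limits for x of n are the 0.025 quantile of Beta(x, n − x + 1) and the 0.975 quantile of Beta(x + 1, n − x).
- Ten related events in ten Veterans: 10/50 = 20%, CI 10.0-33.7%.
- Ten related events in two Veterans: 2/50 = 4%, CI 0.5-13.7%.

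The planned share is identical in these two cases.

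**Step 4. No related events.** The upper limit of the two-sided 95% interval is 1 − 0.025^(1/n).
- n = 50: 7.1%.
- n = 45: 7.9%.
- n = 40: 8.8%.

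The value at 40 is an extreme. It requires all 10 expected dropouts (50 − 40) to leave before starting the program, whereas GROUP1 starts immediately after randomization.

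**The case against.** The best defence is that Section G does not exclude a per-Veteran summary. Safety is listed among the feasibility outcomes, the general sentence permits counts and percents, and the relatedness share is introduced as an addition to other summaries. This is fair as far as it goes. A reader might infer that the plan rules out participant-level reporting, and the documents do not support that. But the general sentence neither names adverse events nor sets a denominator, and the only specific sentence sets one in events. The gap in specification remains.

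Second, dilution misleads mainly when the percentage is printed alone. Shown as 10/20, 10/40 or 10/100, the ten related events are visible. This stands, and the fix reflects it. Printing the counts still does not show how many Veterans were involved.

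Third, the size of the effect is hypothetical. The remark about exacerbations concerns treatment response and drop-out, not adverse-event frequency. Section E describes routine event checks at telerehabilitation sessions, with no equivalent described for the waitlist period or for GROUP1 after week 12. How many unrelated events would be recorded is unknown. This stands, so the figures above are illustrations and not forecasts.

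Fourth, no safety threshold or go/no-go rule depends on the statistic. A reader might infer that the gap could reverse a prespecified conclusion or that it puts participants at risk. Neither follows: no such conclusion is specified, events are recorded with severity and relatedness, and they are reviewed monthly. The per-Veteran figure could still be produced at reporting. What is missing is the commitment to report it and its definition.

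**Conclusion.** The point holds as a reporting gap on a named aim that is cheap to close. The one adverse-event statistic in the plan depends on the number of unrelated events, does not show how many Veterans had a related event, and carries no upper limit on risk per Veteran. The adjacent Aim 1 outcomes already use a per-Veteran percent and an exact interval.

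The dependence on unrelated events follows from R / (R + U) for any positive R. Its size here rests on assumed counts: between 50% and 10% for the same ten related events, which could reflect 20% or 4% of 50 Veterans. The upper limit with no related events needs only the number of starters: 7.1% at 50, and no more than 8.8% if as few as 40 start. The plan contains no arithmetic error on this point.

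**What to change.** In Section G, Aim 1, add the number and percent of Veterans who start the program and have at least one possibly, probably or definitely related adverse event during their 12-week program period (weeks 0-12 for GROUP1, weeks 12-24 for GROUP2). Attach the exact binomial 95% interval already used for Aim 1. State the denominator, which may be below 50 if some GROUP2 Veterans leave before starting. Give the same summary by severity (mild, moderate, severe).

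Keep the planned related share beside it, always printed with its numerator and denominator.

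The cost is a few lines of text and a little more analysis of data already due to be collected, with no new visits, questions or staff. The intervals will be wide with 40 to 50 Veterans, which is an honest picture for a pilot.

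### Randomisation is stratified by sex but the Aim 2 rank-sum test ignores sex: type I error is safe, and some power is lost only if sex is related to change

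*Combined protocol and SAP*

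**What the plan says.** Section D (Study Design and Research Methods) allocates 50 participants to GROUP1 or GROUP2 "using computer-generated random blocks of 2 and 4, stratified by sex". Sex is the only stratification factor named.

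Section G (Data Analysis Plan, Aim 2) takes "the median change from baseline to 12 weeks for those randomized to the intervention", which "will be compared between the groups using a Wilcoxon rank-sum test for each outcome of interest", with 7-day average step count as primary. The general paragraph of Section G adds that "hypothesis tests will be two-sided, assuming an alpha level of 0.05". Nowhere does the document mention a stratified test, an adjustment for sex or any other covariate.

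The population description plans 25 per group and 40 completers at 20% attrition. It also says that "the Veteran population is predominantly male and Caucasian, which will be reflected in the enrollment", without giving a percentage. No effect size, SD or power is stated for Aim 2. Section G reports SDs of change with confidence intervals and says of them: "These estimates and the CIs will inform sample size calculations for a future effectiveness trial".

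**The concern.** Blocked allocation within sex keeps the arms close to balanced on sex. The ordinary rank-sum test takes its null variance from unrestricted allocation, so it allows for chance sex imbalances that the design largely prevents. If men and women change by different amounts, that between-sex variation stays in the test's variance although it can hardly affect the comparison. The test then rejects less often than 5% under the null and less often than it could under a real effect. With about 40 participants analysed, the plan would give up part of what the stratification provides. If sex is unrelated to change, nothing is lost.

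**Working it through.** **The plan's own figure.** 40 / (1 − 0.20) = 50 and 50 × 0.80 = 40, so the stated numbers agree. There is no stated power to reproduce.

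**Inputs from the document.** 50 randomised; blocks of 2 and 4 within sex; 20% loss; two-sided alpha 0.05.

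**Assumed inputs.** 40 analysed at 12 weeks (Section G attaches N=40 to the pooled intervention completers, not to this comparison); treatment effect 0.9 SD, chosen because a two-sample comparison with 20 per arm then has about 81% power; share of women p; sex effect g on the change score, in within-sex SDs; normal change scores.

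**Approximation.** With exact balance within sex, an unstratified test uses a variance too large by the factor 1 + p(1 − p)g². Its critical value on the correct scale is c = 1.96 × √(1 + p(1 − p)g²). The standardised treatment effect is 0.9 × √(20 × 20 / 40) = 2.846, so a stratified test has power Φ(2.846 − 1.96) = 81.2%. The unstratified error rate is 2(1 − Φ(c)) and its power is Φ(2.846 − c).

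| p | g | factor | c | error rate | power | loss (points) |
|---|---|---|---|---|---|---|
| 0.10 | 0.5 | 1.0225 | 1.982 | 4.8% | 80.6% | 0.6 |
| 0.10 | 1.0 | 1.09 | 2.046 | 4.1% | 78.8% | 2.4 |
| 0.20 | 0.5 | 1.04 | 1.999 | 4.6% | 80.2% | 1.1 |
| 0.20 | 1.0 | 1.16 | 2.111 | 3.5% | 76.9% | 4.3 |
| 0.20 | 1.5 | 1.36 | 2.286 | 2.2% | 71.2% | 10.0 |

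This treats the balance as perfect and uses means rather than ranks, so it was checked by simulation.

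**Simulation.** 6,000 trials per setting, blocks of 2 and 4 within sex, random 20% loss. Simulation error is about 0.3 points for error rates and 0.55 for power. Plain rank-sum versus sex-stratified Wilcoxon (van Elteren):

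| Women | Sex effect | Error rate | Power |
|---|---|---|---|
| 5% | 1 SD | 4.9% vs 5.4% | 74.6% vs 75.4% |
| 10% | 1 SD | 4.4% vs 5.1% | 73.9% vs 75.7% |
| 20% | 1 SD | 3.5% vs 4.5% | 71.6% vs 75.6% |
| 10% | 2 SD | 3.3% vs 4.8% | 67.7% vs 76.2% |
| 20% | 2 SD | 2.3% vs 4.9% | 58.5% vs 75.6% |

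At 0.5 SD with 5% to 20% women, the two powers differ by under 1 point. With no sex effect the order reverses: van Elteren is about 1 to 1.6 points lower. With the number of women fixed at 10 (4,000 trials per setting), power was 71.6% vs 75.0% at 1 SD and 65.8% vs 75.6% at 1.5 SD, losses of 3.4 and 9.8 points. If all 50 are analysed, 20% women and 1 SD give 81.8% vs 85.3%, a loss of 3.5 points.

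**Small female stratum.** A stratum with only one arm represented adds nothing to a stratified test. Take block sizes 2 and 4 as equally likely and each woman as retained with probability 0.8.
- Two women: they fall in different arms with probability 1 − ½ × ⅓ = 5/6, and both are retained with probability 0.64. The stratum is one-armed or empty in 1 − (5/6 × 0.64) = 47% of trials (about 46% in simulation).
- Three women: they always split 2:1. The stratum is one-armed or empty in 1 − 0.8 × (1 − 0.2²) = 23% of trials (23% in simulation).

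**The case against.** The strongest case is that the loss hardly matters in the trial described. The sample will be mostly male, and with 2 to 5 women and a 1 SD sex effect about 0 to 2 points of power are at stake. The tested quantity is change, so sex differences in the level of steps, sit to stand or arm curl largely cancel. A sex effect of 1 SD or more on change is a strong assumption with no support in the document. Aim 2 is a preliminary assessment, its hypothesis speaks of a trend, and the planning output is SDs with confidence intervals, none of which depends on this test. All of that stands, and it is why the point is minor.

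A reader might infer that the test is invalid or gives too many false positives. It does not; the error moves in the safe direction. A reader might also infer that error rate and power fall whatever the data. They fall only if sex is related to change; if it is not, the stratified test is slightly the less powerful.

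What survives is that sex was chosen as the one factor to balance on, the analysis does not use it, and the trade favours using it. The cost is about 1 to 2 points if sex is irrelevant; the gain is about 3 to 10 points with 10 women and a 1 to 1.5 SD effect.

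**Conclusion.** The mismatch between Sections D and G is real, and its consequence is conditional and one-sided: no inflation of type I error, and some loss of power if sex is related to the change score. Under the assumed 0.9 SD treatment effect with 40 analysed, the loss is:
- negligible at a sex effect of 0.5 SD or less;
- about 0 to 2 points with 2 to 5 women and 1 SD;
- about 3 to 4 points with 10 women and 1 SD;
- about 10 points with 10 women and 1.5 SD.

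The number of women, the sex effect and the treatment effect are all assumptions. The document therefore does not support a claim that the pilot is underpowered or its sample size wrong. This is a minor refinement.

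It applies directly to the Aim 2 outcomes other than step count. The ActiGraph paragraph under Outcomes in Section D schedules GROUP2's wear at weeks 12 and 24 only, so no baseline-to-12-week change in steps exists for that group. Neither form of the test can be computed for the primary outcome until that paragraph and Section G agree.

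**What to change.** In Section G, Aim 2, replace the rank-sum test with a rank test stratified by sex. The aligned-rank version is preferable, since it loses under about 1.5 points of power if sex is irrelevant. Otherwise use van Elteren, which is available in the SAS the plan names (PROC FREQ, CMH2 with SCORES=MODRIDIT).

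Add one sentence fixing the fallback in advance: if either sex stratum has no analysed participants in one arm, the unstratified rank-sum test is used. The trigger depends only on who is analysed in each arm, not on the test result.

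For step count, first reconcile the ActiGraph schedule in Section D with the comparison in Section G.

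The cost is one or two sentences, with no change to recruitment, randomisation or data collection for the other outcomes, and a small loss of power if sex proves unrelated to change.
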